#### **Statistical Considerations**

#### Sample Size

Specific Aims 1 and 2 of the study are to test the feasibility of exogenous progesterone for cannabis withdrawal (1), and determine its efficacy in attenuating withdrawal symptoms in heavy-cannabis-using women (2). The maximum attainable sample size of 40 (20 per condition) will yield stable levels of plasma progesterone and estimates of cannabis withdrawal symptoms across groups.

#### Statistical Analyses

The hypothesis associated with Specific Aim 1 concerns the feasibility of exogenous progesterone in cannabis using women. It is hypothesized that participants receiving progesterone compared to placebo during the early follicular phase will demonstrate plasma progesterone levels comparable to the average range found in the mid-luteal phase. The hypothesis associated with Specific Aim 2 concerns the efficacy of exogenous progesterone in attenuating cannabis withdrawal symptoms in female cannabis users. It is hypothesized that participants receiving progesterone compared to placebo will show reductions in cannabis withdrawal symptoms. The exploratory aim is concerned with the impact of progesterone on cognitive performance. It is hypothesized that participants receiving progesterone compared to placebo will demonstrate better cognitive function at the end of the study period. These hypotheses will be tested using a random effects mixed model for repeated measures; this methodology allows the estimation of the variance associated with a random intercept for each subject and can accommodate partially missing data (Brown and Prescott, 1999). In addition to the primary analyses, contrasts of pertinent baseline characteristics will be performed between groups. If the groups differ significantly on any of these baseline characteristics, the corresponding variables will be used as covariates in the above analyses. To note, all analyses will be considered preliminary in nature, and will need to be confirmed by a larger study.

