#### D. RESEARCH DESIGN AND METHODS

#### **D1. General Procedures:**

**Study Overview.** The proposed study will investigate the effect of exogenous progesterone on cannabis withdrawal among female cannabis users. Forty heavy-cannabis-using women will be randomized based on nicotine dependent status to receive placebo or progesterone (200mg bid) over a consecutive 5-day period during the early follicular phase of their menstrual cycle and asked to abstain from cannabis. Menstrual phase will be determined by onset of menses and ovarian hormone levels. Following screening, within 3 days of onset of menses, participants will undergo study visit 1 (day 1 abstinence) which includes biochemical, subjective, and cognitive performance assessments, randomization, and medication instructions; they will take their first medication dose that evening. Participants undergo study procedures on study days 2-4 at home and will return to the clinic on study day 5 for repeat assessments. Salivary progesterone and estradiol levels will be collected daily, and cannabis withdrawal will be assessed twice daily, concurrent with medication adherence procedures. Primary outcomes include progesterone levels and cannabis withdrawal symptoms.

**Recruitment.** Women who use cannabis daily or near daily will be recruited from the community based on previously successful techniques used over the past 20 years by the research team. This will include a mix of community, print, and online advertising.

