Adherence Monitoring. Participants will record themselves taking their morning and evening medication doses and then submit these videos to research staff via RedCap survey. Subjects may use their personal smartphones for video submission. If they do not have a smartphone, one will be loaned to them during the course of the study, as video submissions may only be completed on a smartphone (cannot be completed on a computer). A survey link will be sent to the subject via text message twice daily. Video capture will occur as part of the RedCap survey. Videos are automatically stored on some Android smartphones, and participants will be informed of that so they can delete the files, if necessary. Participants using iPhones (and using loaner iPhones from our group) will not have stored videos on their phone and nothing will need to be deleted.

**Ovarian Hormones:** *Progesterone* and *Estradiol* will be measured from salivary samples collected using the passive drool method. Saliva samples will be collected daily; in the lab on days 1 and 5, and at home on days 2-4. Participants will be trained on how to collect and store the samples by study personnel on study day 1.

**Cannabis Withdrawal.** The *Cannabis Withdrawal Scale (CWS; Allsop et al., 2011)* will be used to assess cannabis withdrawal symptoms. CWS is a 19-item self-report measure that assesses cannabis withdrawal symptoms in the past 24 hours (sample items: I felt restless; I had a headache; I had trouble getting to sleep at night) on a 10-point Likert scale (0=Not at All to 10=Extremely). To establish a baseline withdrawal score, the CWS will be administered in person on study day 1. CWS will then be administered once on study days 1 and 5, and twice daily on study days 2-4 as part of the RedCap medication adherence survey that will be sent via text message to the participant. Participants will be asked to respond with reference to the past 12 hours.

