**Consent and Screening Interview.** Potential participants will present to the Addiction Sciences Division (ASD) Research Clinic and will be given a full description of the study procedures and asked to read and sign an IRB-approved informed consent form. The Mini-International Neuropsychiatric Interview (M.I.N.I.; Sheehan et al., 1998) will assess exclusionary psychiatric and substance use diagnoses during the past year, including frequency of cannabis use. Participants will provide a urine sample, which will first be tested for pregnancy and subsequently for substance use. Past month cannabis and all other substance use will be assessed using the Timeline Follow-Back (TLFB; Sobell & Sobell, 1992). A medical history and physical exam will be conducted to ensure that the individual is eligible to participate. Participants will provide expected date of menses onset for study personnel to follow-up prior to study day 1 visit.

**Tracking period between screening and study day 1 visit:** Following screening visit participants will be asked to track their menstrual cycle and contact the clinic upon menses onset. Study personnel will reach out to participants 3 days prior to expected onset provided at screening as a reminder. Upon menses onset, participants will schedule study day 1 visit to occur within 3 days, or on Monday if onset occurs on the weekend (Friday-Sunday). *Study day 1 must occur on Monday, Thursday, or Friday in order to assure in-person visit on study day 5.* Participants will be asked to begin abstinence on Study Day 1.

**Study day 1 visit:** Participants will present to ASD and undergo urine toxicology, Breathalyzer, saliva testing, and TLFB. After all inclusion criteria and no exclusion criteria have been satisfied, the participant will be randomized to either the experimental (progesterone 200mg bid) or control (placebo) condition based on nicotine dependent status (FTND score of 4 or greater, versus 3 or below). Participants will then provide a saliva sample for progesterone and estradiol quantification, followed by cognitive testing, and then self-report assessments (see *Instrumentation* section). Participants will then receive medication instructions and review medication adherence procedures (see *Adherence* section). Participants will be instructed to take first dose of medication at 9:00pm that evening to minimize sedation. Participants will then be compensated and discharged.

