#### Example study day 1 timeline

Time	Procedure	Duration
9:00 am	Saliva, breathalyzer, utox	15 mins
9:15	TLFB	15 mins
9:30	Saliva sample (hormones)	5 mins
9:35	Cognitive testing	15 mins
9:50	Self-report assessments (FrSBe, CWS, PANAS-X, CUDIT-R)	20 mins
10:10	Medication instructions	20 mins
10:30	Compensate/discharge	
9:00 pm	First medication dose, CWS (at home)	

**Study days 2-4:** Participants will be prompted by RedCap to complete medication adherence and CWS at 9am and 9pm. Each day participants will schedule a Skype/FaceTime call with study personnel to conduct saliva testing and adverse event assessment. Should an adverse event occur, trained personnel will assess via video conference to determine necessary procedures. Participants will also provide a saliva sample for hormone testing. Participants will be provided with labeled tubes for saliva collection and storage. They will fill out the date and time and place in the freezer to be stored until study day 5 when they will bring to ASD clinic for testing.

**Study day 5 visit:** Participants will present to the ASD clinic by 10am for final study visit. They will undergo saliva testing, urine toxicology, Breathalyzer, and TLFB, followed by hormone saliva sampling and cognitive testing. Participants will be debriefed, compensated, and discharged.

Time	Procedure	Duration
9:00am	Last medication dose, CWS (at home)	
9:00	Saliva, breathalyzer, utox	15 mins
9:15	TLFB	15 mins
9:30	Saliva sample (hormones)	5 mins
9:35	Cognitive testing, FrSBe	15 mins
9:50	Compensate/debrief	10 mins
10:00	Discharge	

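### Aim 1 is stated on plasma progesterone although every hormone sample is saliva, and no salivary luteal interval or comparison of active-arm levels with one is specified

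*Combined protocol and SAP*

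**What the plan says.** **Outcome.** The Study Overview in D1 states: "Primary outcomes include progesterone levels and cannabis withdrawal symptoms". Hypothesis 1 (Section A) sets the target as the luteal phase and adds that treatment will be well tolerated.

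**Statistical sections.** Statistical Analyses says that women given progesterone rather than placebo in the early follicular phase "will demonstrate plasma progesterone levels comparable to the average range found in the mid-luteal phase". Sample Size says that 40 women, 20 per condition, "will yield stable levels of plasma progesterone". One random-effects mixed model for repeated measures is named for all hypotheses.

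**Sampling.** D1: "Salivary progesterone and estradiol levels will be collected daily". D2, under Ovarian Hormones, says that both hormones "will be measured from salivary samples collected using the passive drool method". For the Day 1 visit: "Participants will then provide a saliva sample for progesterone and estradiol quantification". For Days 2-4: "Participants will also provide a saliva sample for hormone testing". The Day 5 timeline, the assessment table and the compensation schedule also refer to saliva for hormones.

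**Range.** The one numerical luteal range, 2-20 ng/ml, is in the dosing rationale in D2. It comes with a reference to earlier studies and does not say whether it applies to plasma, serum or saliva.

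**The concern.** The statistical sections name a variable that the planned procedures will not produce. The analyst will have salivary values and no salivary target to judge them against.

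There is a second gap. Hypothesis 1 is about where active-arm levels lie relative to a range. The only comparison put into words is with placebo, and the placebo women are in the early follicular phase. Showing that treatment raises progesterone above that level is a weaker statement than showing that it reaches luteal values.

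At stake is whether half of Hypothesis 1 can be answered; the other half, tolerability, is unaffected. D2 and Potential Study Limitations express confidence in the levels and effect of the regimen, but from studies in cocaine and nicotine users. Aim 1 is where that expectation is checked in cannabis users.

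**Working it through.** The plan gives no power, effect size or SD for progesterone, and 40 is described as the largest attainable sample, so there is no figure to reproduce. The point rests on setting the sections side by side.

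**1. Matrix**

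| Place | Matrix for progesterone |
|---|---|
| Sample Size; Statistical Analyses | Plasma |
| D1 Study Overview; D2 Ovarian Hormones | Saliva |
| D2 Day 1 visit; Days 2-4; Day 5 timeline | Saliva |
| Assessment table; compensation schedule | Saliva, no blood row |
| Section E, Sources of Materials | Breath and urine only |
| Section E, Potential Risks | No blood-draw risk |

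The assessment table and timelines are the real evidence that no blood is taken. The Section E materials list is weak evidence, because it omits saliva too.

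**2. Target.** Hypothesis 1 says luteal, and Statistical Analyses says mid-luteal. Neither gives numbers. The 2-20 ng/ml range is not carried into the outcome or the analysis.

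**3. Comparison.** The hypothesis has the form: active-arm level lies in [L, U]. The comparison in the text has the form: active differs from placebo. The second does not imply the first, wherever L and U lie. The contrast itself is not written out, and the same model could give active-arm means, so this is under-specification.

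**4. Timing.** Day 1 is a pre-dose baseline: the sample is taken at the visit, and "Participants will be instructed to take first dose of medication at 9:00pm that evening". On Days 2-4 doses are at 9am and 9pm but no hormone-sample time is fixed, so a sample could fall anywhere from 0 to 12 hours after a scheduled dose. The Day 5 example samples at 9:30 after a 9:00 dose, which is 30 minutes. Daily means may therefore reflect different times since dosing.

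**5. Illustration (assumed inputs, lower limit only; the point does not need it).** Let L be the lower limit of the interval and s the SD of natural-log progesterone between women on one day, assumed 0.4-0.8, with 20 women per arm.

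- Placebo contrast: t = ln(active/placebo) / (s × √(2/20)), 38 df. With placebo 0.15 L, s = 0.6 and an active mean of 0.5 L (below range), t = ln(3.33)/(0.6 × 0.316) = 6.35, p = 1.9 × 10⁻⁷. With placebo 0.15 L, s = 0.8 and an active mean of 1.5 L (above L), t = ln(10)/(0.8 × 0.316) = 9.10, p = 4 × 10⁻¹¹. Both are clearly significant.
- This depends on the inputs. With placebo 0.30 L, active 0.5 L and s = 0.8, t = ln(1.667)/(0.8 × 0.316) = 2.02, p = 0.051.
- Active-arm 95% CI: geometric mean divided and multiplied by exp(2.093 × s/√20), which is 1.21 at s = 0.4 and 1.45 at s = 0.8.
- At s = 0.8, a mean of 0.5 L gives 0.34-0.73 L (below L) and 1.5 L gives 1.03-2.18 L (above L). Means of 0.7 L (0.48-1.02 L) and 1.4 L (0.96-2.04 L) both straddle L and give no clear answer.

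**The case against.** **Plasma is a slip of wording.** The operational sections agree on saliva, so nobody will be in doubt about which samples are assayed. This stands: the mismatch alone is a wording correction. Correcting it still leaves no salivary interval and no stated comparison with one.

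**The plan does not misuse the placebo contrast.** A reader might infer that a significant placebo difference is to be taken as confirming Hypothesis 1. The documents do not say so. Statistical Analyses words the claim as comparability with a range, and the named model can give active-arm means. What can be said is that no such estimate is specified, which leaves the weaker reading open.

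**The range is given in D2.** A reader might go further and infer that 2-20 ng/ml is a plasma range being wrongly applied to saliva. The text supports neither use: the range has no matrix label and is not linked to the analysis.

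**Any numbers are chosen.** This stands. The documents give no SD, placebo level or salivary limit. The illustration does not show that the contrast is always significant, and it says nothing about the upper limit.

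**It is a 40-woman pilot.** Statistical Analyses calls every analysis preliminary and in need of confirmation in a larger study. That limits the consequence but does not define the target.

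**Conclusion.** The concern holds, at the level of something that should be fixed. The primary hormone outcome is named in a matrix that is not collected, the luteal target has no usable interval, and the only comparison put into words does not by itself address whether active-arm levels reach a luteal range. These conclusions rest on the text and on logic, not on assumed values.

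The size of the problem in practice cannot be stated from the documents. They do not support an inference that active-arm levels are likely to fall short of the range. The 1.21-1.45 CI factor assumes a log-SD of 0.4-0.8 and complete data from 20 women on a given day.

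**What to change.** 1. Replace plasma with salivary in Sample Size and Statistical Analyses, add saliva to the materials list in Section E, and use one target term, luteal or mid-luteal, throughout.
2. Before hormone data are analysed, fix one salivary reference interval for the assay used. Do not apply 2-20 ng/ml to saliva unless its matrix is confirmed.
3. As the Aim 1 range assessment, report active-arm means from the planned mixed model for Days 2-5, with 95% CIs, against that interval. Geometric means from logged values are a reasonable choice that the documents do not require. Treat Day 1 as the pre-dose baseline.
4. Keep the placebo contrast as a separate, supportive statement.
5. Record sample time relative to the last dose, and report or account for it in the range assessment. This is required, because sampling times are not fixed on Days 2-4. Participants already write date and time on the tubes.

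**Cost.** Wording changes, one interval and one table from the model already planned, with no new samples or participants. The documents name no hormone assay, so the interval must come from outside them. The Aim 1 result may look less favourable, and a mean within a factor of about 1.21-1.45 of a limit will be inconclusive. The tolerability part of Hypothesis 1 does not change.

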**Assessment Timeline** 

Participant Compensation. Participants will be compensated for participating in the study. Participants will receive \$40 for screening assessment (\$20 for interview and \$20 for physical exam) and \$50 for study days 1 and 5 visits. Participants will receive \$20 for each completion of medication adherence and CWS. Participants will receive an additional \$30 for each negative saliva cannabis drug screen and \$10 for a positive saliva screening on Days 2-4. Participants will receive \$10 for each salivary hormone sample collected on Days 2-4. Maximum potential compensation is \$420 value in the form of cash. Subjects will be compensated for negative drug screens since it is absolutely crucial to maintain abstinence in order to observe withdrawal symptoms.

Summary of compensation schedule:

	Screening	Day 1	Day 2	Day 3	Day 4	Day 5	
Attendance	\$40	\$50				\$50	
Medication/CWS		\$20	\$40	\$40	\$40	\$20	
Saliva Drug Screen			\$30	\$30	\$30		
Saliva Hormones			\$10	\$10	\$10		
Totals	\$40	\$70	\$80	\$80	\$80	\$70	\$420

**Confidentiality.** Confidentiality will be maintained using procedures that are employed as standard policy. Confidentiality of all research data will be maintained by keeping all data in a locked file. limiting access to the computer database to only study personnel, and by using patient code numbers/initials as opposed to names on all paperwork. Any requests for the release of patient information will be referred to [name].

**Data Management and Reduction.** All paper-based assessments (other than laboratory reports) will be entered into REDCap, a secure, web-based application designed exclusively to support data capture for research studies. REDCap provides an intuitive interface for data entry (with data validation), audit trails for tracking data manipulation, and automated export procedures for data downloading to statistical packages such as SPSS and SAS. Completed assessments will be entered within two weeks after the information has been collected from the subject. Quarterly database management and data integrity audits will be conducted.

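### The efficacy hypothesis rests on nine withdrawal scores with no deciding contrast and only significance-triggered adjustment, so a compliant analysis can include two pre-drug scores and leave out the baseline score.

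*Combined protocol and SAP*

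**What the plan says.** D1, Study Overview, states: "Primary outcomes include progesterone levels and cannabis withdrawal symptoms". No order is given between the two.

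D2, Cannabis Withdrawal, sets the schedule. For the baseline, "the CWS will be administered in person on study day 1"; after that, "CWS will then be administered once on study days 1 and 5, and twice daily on study days 2-4". The example Day 1 timeline puts the second Day 1 score at 9pm at home, together with the first dose.

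Under Statistical Analyses, Hypothesis 2 is that "participants receiving progesterone compared to placebo will show reductions in cannabis withdrawal symptoms". On method: "These hypotheses will be tested using a random effects mixed model for repeated measures". The section mentions a random intercept per subject and tolerance of partly missing data. For Hypothesis 2 it gives no time point, average, slope or change score, no coding of time, no role for the baseline score, and no alpha or sidedness. Only the exploratory cognitive hypothesis has a time point, the end of the study period.

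On covariates, the section compares baseline characteristics between arms and adjusts for those that differ significantly. D3, Self-Report Instruments, separately commits to CUDIT-R as a covariate. Randomisation depends on nicotine dependence (FTND 4 or above against 3 or below), but the analysis text does not mention that stratum.

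**The concern.** A repeated-measures mixed model is a framework that yields many treatment contrasts. The plan's wording allows the group effect over all scores, the mean of post-dose scores, a group-by-time slope or a Day 5 change. These are not equally good tests.

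The all-score group effect is the weakest in one respect. The in-clinic Day 1 score precedes treatment. The 9pm Day 1 score accompanies the first dose and, because participants answer for the past 12 hours, describes the period before it. Both contribute noise and no treatment effect.

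The covariate rule adds to the loss. Under randomisation, any baseline difference is due to chance. At an assumed 5% level, the rule would bring in baseline CWS in about 1 trial in 20, if it counts as a pertinent characteristic at all. The FTND stratum is balanced by design, so it would rarely qualify.

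At stake are avoidable power in a 40-person trial and a clear answer to which number is the Hypothesis 2 result.

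**Working it through.** **1. Number of scores.** From D2: 1 (baseline) + 1 (Day 1, 9pm) + 3 × 2 (Days 2-4) + 1 (Day 5) = 9. Cross-check from Participant Compensation: survey payments of 20 + 40 + 40 + 40 + 20 = 160 dollars, at 20 dollars each, make 8 surveys; with the in-person baseline, 9. Two precede any drug effect, so 7 are post-dose.

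**2. Sample size.** 40 (20 per condition) is given as the maximum attainable, with no alpha, power, effect or SD behind it. There is no stated power to reproduce.

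**3. Assumptions (not in the documents).** Two-sided 5%; SD 1 at each time; no dropout; a 0.8 SD reduction at all seven post-dose scores and none before. Correlation is either exchangeable (0.5 or 0.7) or a random intercept carrying 0.3 or 0.5 of the variance plus serial correlation of 0.7 per 12 hours.

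**4. Formula.** For a summary with true difference δ and between-subject variance v, λ = δ / √(2v/20). Power comes from the noncentral t distribution with 38 df, or 37 df after baseline adjustment.

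Under exchangeable correlation ρ:
- All-score mean: δ = 0.8 × 7/9 = 0.622; v = (1 + 8ρ)/9.
- Post-dose mean: δ = 0.8; v = (1 + 6ρ)/7.
- Baseline-adjusted post-dose mean: δ = 0.8; v = (1 + 6ρ)/7 − ρ².

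At ρ = 0.5, v = 5/9 = 0.556, 4/7 = 0.571 and 0.571 − 0.25 = 0.321. For the serial structures, v is the same quadratic form using their covariance matrix.

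| Structure | All-score: v, λ, power | Post-dose: v, λ, power | Adjusted post-dose: v, λ, power |
|---|---|---|---|
| Exchangeable 0.5 | 0.556, 2.64, 73% | 0.571, 3.35, 90% | 0.321, 4.46, 99% |
| Exchangeable 0.7 | 0.733, 2.30, 61% | 0.743, 2.94, 82% | 0.253, 5.03, 99.8% |
| Intercept 0.3 + serial | 0.612, 2.52, 69% | 0.663, 3.11, 86% | 0.460, 3.73, 95% |
| Intercept 0.5 + serial | 0.723, 2.32, 62% | 0.759, 2.90, 81% | 0.391, 4.05, 98% |

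Simulation of the same comparison gave 61-74%, 80-91% and 95-100%.

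**5. Contrast chosen after seeing the data.** With one named contrast, the simulated false-positive rate stays at about 5%. If either of two may count (adjusted post-dose mean, slope), simulation gives about 9%. Two independent tests would give 1 − 0.95² = 9.75%. Adding Day 5 change gives about 11-12%; three independent tests would give 1 − 0.95³ = 14.3%, and the correlation between contrasts lowers this. Counting only results in progesterone's favour, the range for two or three contrasts is 4.4-6.0%, against 2.5%.

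**6. Cost of the proposed contrast.** If the effect instead grows to 1 SD on Day 5, power is 80-96% for the adjusted post-dose mean and 73-100% for the slope, depending on the correlation structure.

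**The case against.** The strongest reply is that this is a pilot. Statistical Analyses calls every analysis preliminary and in need of confirmation, the sample size is simply what can be attained, and confirmatory error control is never claimed. That stands, and it limits how much weight any p-value carries. It does not say which estimate is the Hypothesis 2 estimate, and the section still says the hypotheses will be tested.

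A second reply is that most of the power gain comes from baseline adjustment and less from the choice of contrast. This is largely right. Adjusting the mean of the eight scores after baseline, with the 9pm Day 1 score kept in, gives δ = 0.8 × 7/8 = 0.70. With v = (1 + 7ρ)/8 − ρ², power is 97% at ρ = 0.5 and 99% at ρ = 0.7. So the covariate rule matters at least as much as the unnamed contrast. The calculations also use subject-level summaries in place of the fitted mixed model.

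A reader might infer more than the documents support:
- **That the candidate contrasts would give opposite answers.** This depends on an assumed shape of effect over time. The typical disagreement is that one contrast reaches significance and another does not. Potential Study Limitations calls withdrawal protracted and does not describe it easing within five days.
- **That the plan's error rate is doubled.** The inflation arises only if the contrast is chosen after looking at the data. Nothing in the plan says that it will be.
- **That the hypothesis is worded in two conflicting ways.** Statistical Analyses uses attenuation and reduction for the same hypothesis in adjacent sentences, evidently as synonyms.

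**Conclusion.** The concern holds as a gap with a concrete and better alternative. The plan names no deciding contrast for a primary outcome. Its covariate rule would usually leave out the baseline score and the randomisation stratum. Under the stated assumptions, an analysis that fully complies with the plan could have 61-74% power where the same data support 95-100%. Dropping the two pre-drug scores and adjusting for baseline account for the difference.

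The false-positive risk is secondary and conditional. It is roughly double the nominal rate for two or three candidates, and only if the choice follows the data. All these figures rest on an assumed alpha, effect size, effect shape and correlation, because the documents give none of them. The count of nine scores, the two pre-drug scores and the missing contrast come directly from the text.

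**What to change.** Add to Statistical Analyses, before any outcome data are examined by arm:

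- The primary test of Hypothesis 2 is one two-sided 5% contrast from the repeated-measures model: the progesterone-minus-placebo difference in mean CWS total over the seven post-dose scores (Day 2 9am to Day 5 9am), reported with its 95% CI.
- It is adjusted for the in-person Day 1 CWS, the FTND stratum and CUDIT-R. For this test, that fixed set replaces the rule that selects covariates by baseline significance. This also reconciles the section with the CUDIT-R commitment in D3.
- Group-by-time, Day 5 and other contrasts are supportive, whatever their p-values.

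The cost is a few sentences, with no added visits, samples or participants. The downside is some loss of power relative to the slope or Day 5 contrast if the effect builds only towards Day 5 (80-96% against 73-100% for the slope, as above); the supportive contrasts would still show such a pattern. The seven-score mean is one defensible choice. If the sponsor expects a late effect, another contrast could be named instead, provided it is a single one fixed in advance.

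### Covariates are to be chosen by baseline significance tests, which cannot identify prognostic variables; pre-specify the FTND stratum and each outcome's Day 1 value, and carry CUDIT-R into the analysis section

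*Combined protocol and SAP*

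**What the plan says.** The Statistical Analyses section proposes a random-intercept mixed model for all hypotheses (progesterone level, cannabis withdrawal, cognition). It adds between-group tests of unlisted baseline characteristics, with this consequence: "If the groups differ significantly on any of these baseline characteristics, the corresponding variables will be used as covariates in the above analyses". It gives no threshold and names no fixed covariate. It calls all the analyses preliminary.

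Other sections bear on the choice of covariates:

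- **Randomisation factor.** In D1, Study Overview, participants "will be randomized based on nicotine dependent status to receive placebo or progesterone". D2, Study day 1 visit, defines the factor: "based on nicotine dependent status (FTND score of 4 or greater, versus 3 or below". I read this as stratification. No section makes it a model term.
- **Day 1 withdrawal score.** D2 says "To establish a baseline withdrawal score, the CWS will be administered in person on study day 1", and then "CWS will then be administered once on study days 1 and 5, and twice daily on study days 2-4". No section says whether the Day 1 score is a covariate or the first repeated measure.
- **Timing.** "Participants will be asked to begin abstinence on Study Day 1". The example Day 1 timeline puts "Self-report assessments (FrSBe, CWS, PANAS-X, CUDIT-R" at 9:50 am and "First medication dose, CWS (at home" at 9:00 pm.
- **CUDIT-R.** D3, Self-Report Instruments, already declares it a covariate. The Statistical Analyses section does not repeat this.

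**The concern.** Covariates earn their place by predicting outcome. A baseline test between randomised groups asks something else: whether chance produced a difference. The answer says nothing about prediction.

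A variable used in randomisation is kept close to balance, so the rule would pass over the very factor the design singles out. A strongly predictive Day 1 score would be left out in about 19 trials in 20. A useless variable would enter as often as a useful one.

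At stake are a model that cannot be known in advance and possibly lost precision. D3's commitment to CUDIT-R also needs reconciling with a section that admits covariates only on significance. The sample size section presents 40 women as the most that can be obtained, so lost precision cannot be bought back by recruiting more.

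**Working it through.** **Plan's own figure.** There is none to reproduce. The sample size section gives 40 (20 per condition) with no alpha, power, effect size, SD or correlation. Everything below assumes two-sided alpha 0.05, complete data and a per-score SD of 1.

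**1. What the rule selects.** In simulation (20 per arm), the Day 1 score was flagged in 4.8% to 5.1% of trials at every correlation with outcome from 0 to 0.8. With m independent candidates, the chance of at least one flag is 1 − 0.95^m: 23% for m = 5 and 40% for m = 10. For the FTND stratum, assume 16 of 40 women are dependent. Even a 10/6 split gives Fisher p = 0.33.

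**2. Variance of the treatment contrast** for the mean of the seven scores after the first dose (six on Days 2–4, one on Day 5). Let r be the correlation among later scores and b their correlation with Day 1. In units of 2·SD²/n:

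- Day 1 ignored: P = (1 + 6r)/7
- change from Day 1: P + 1 − 2b
- adjusted for Day 1 with c covariates: (P − b²) × 37/(37 − c)

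The last factor is the cost of estimating covariates at N = 40: 1.028, 1.057 and 1.088 for c = 1, 2 and 3.

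Example, b = r = 0.5. P = 4/7 = 0.571. With c = 3 the adjusted value is (0.571 − 0.25) × 1.088 = 0.350. For an effect of 0.5 SD, the standard error is √(2 × 0.571/20) = 0.239 unadjusted and √(2 × 0.350/20) = 0.187 adjusted. The effect is then 2.09 and 2.67 standard errors, against critical values near 2.02 and 2.03.

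**3. Power at 0.5 SD (simulation).** The adjusted column has three covariates, of which only Day 1 is prognostic.

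| b, r | Rule | Adjusted | Change score |
|---|---|---|---|
| 0.3, 0.3 | 69% | 76% | 41% |
| 0.5, 0.5 | 54% | 73% | 53% |
| 0.7, 0.7 | 45% | 83% | 75% |
| 0.1, 0.5 | 53% | 51% | 26% |
| 0.3, 0.5 | 53% | 57% | 35% |

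The last two rows matter. Abstinence starts on Day 1 and the baseline CWS is taken that morning with a 12- or 24-hour recall, so it may mostly describe time before abstinence. With b = 0.1, the variance ratio of adjusted to unadjusted is (0.571 − 0.01) × 1.088/0.571 = 1.07. With b = 0.3 it is (0.571 − 0.09) × 1.088/0.571 = 0.92. Three covariates break even at b of about 0.21 (r = 0.5) to 0.25 (r = 0.7).

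**4. Type I error of the rule**, one candidate covariate, b = r = 0.3/0.5/0.7: 4.4/3.7/3.1%.

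**5. Linear slope.** A between-subject covariate does not alter a within-subject contrast when data are complete. In 30 simulated fits the standard error of treatment-by-time was 0.0855 with and without adjustment. Removing Day 1 as a time point does cost information. With time in days, the time sum of squares is 7.0 for the seven later scores, 12.47 with the in-clinic Day 1 score (1.8 times) and 15.0 with the 9 pm score as well (2.1 times).

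**6. FTND.** If half the women are dependent and differ by 0.3/0.5/0.8 SD, omitting the stratum widens the confidence interval by 1/3/8% and lowers type I error to 4.8/4.4/3.5%.

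**The case against.** Four objections deserve weight.

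- **The plan already has a route to adjustment.** D3 declares CUDIT-R a covariate, and protocol and SAP are one document. This stands: for CUDIT-R the problem is a missing cross-reference. A reader might infer that the plan pre-specifies no covariate at all; D3 shows otherwise.
- **The large power losses assume a contrast the plan does not state.** A reader might take 45% against 83% as the price of the rule. That comparison needs a post-dose mean that ignores Day 1 unless it is flagged, together with a strong baseline correlation. A repeated-measures model for reductions in symptoms can equally be read as keeping Day 1 as an occasion. The comparator is then the change score, or a slope with nothing to gain. This also stands, and it makes the size of the loss undetermined.
- **Adjustment is not free.** Each non-prognostic covariate adds about 3% to the variance (9% for three). With a weak baseline, the fixed model can do slightly worse than the rule.
- **This is a pilot, and its analyses are called preliminary.** That limits the harm. It does not justify the rule, since the Future Studies section looks ahead to fully powered trials.

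A reader might also infer that data-driven covariate selection inflates false positives. The calculations do not show that: with one candidate the rule is conservative. An unlisted set of candidates was not tested, so no broader assurance is offered either.

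**Conclusion.** The criticism of the rule holds at every correlation tried: baseline significance carries no information about prognosis, and the randomisation factor would almost never be selected. The loss is one of precision and predictability of the model.

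Its size cannot be fixed from the documents. Under the stated assumptions, pre-specification ranges from a loss of about 2 power points (weak Day 1 score) to a gain of 7 to 38 points (common correlation 0.3 to 0.7, Day 1 otherwise ignored). Against a change score the gain is 35, 20 and 8 points at 0.3, 0.5 and 0.7. For a slope with complete data it is nil. The FTND gain is small; the main reason to include the stratum is that the analysis should reflect the randomisation.

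This should be changed, but the stakes are modest. Whether the Aim 2 contrast is a post-dose mean or a change over time is a separate, secondary point, although it decides which of these figures applies.

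**What to change.** Delete the significance-test sentence, show baseline characteristics descriptively, and add wording such as:

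> Models for progesterone level, CWS and each cognitive outcome will include treatment, the FTND randomisation stratum (4 or more versus 3 or below) and that outcome's own pre-dose Day 1 value. The Day 1 value enters either as a covariate or as the first time point with a common mean in both arms, not both. The CWS model also includes CUDIT-R.

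Then state:

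- whether CUDIT-R applies to progesterone and cognition, and whether PANAS-X is a covariate or descriptive only;
- the Aim 2 contrast. If it is a post-dose mean, list the assessments averaged and say how the 9 pm Day 1 score, recorded with the first dose, is treated. If it is change over time, keep Day 1 as a time point with a common mean;
- for cognition, measured only on Days 1 and 5, that Day 5 is compared by ANCOVA on Day 1 or by the equivalent two-occasion model.

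The cost is SAP wording: every variable is already collected. Statistically it is two or three degrees of freedom, with variance up by about 6% or 9% if none of the two or three covariates is prognostic. The list should stay this short at 40 women.
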